5. SELECTION OF POPULATION AND WITHDRAWAL CRITERIA

Specific information regarding warnings, precautions, contraindications, adverse events, and other pertinent information on the GSK investigational product or other study treatment that may impact subject eligibility is provided in the Investigator's Brochure and Supplement [GlaxoSmithKline Document Number: CM2003/00010/08 and GlaxoSmithKline Document Number: 2014N200212_00].

Deviations from inclusion and exclusion criteria are not allowed because they can potentially jeopardize regulatory acceptability or subject safety. Therefore, adherence to the criteria as specified in the protocol/LAP is essential.

All requests for continued treatment will be submitted to GSK using the LAP Application Form. The Lead Mepolizumab Medical Advisor for the mepolizumab EGPA programme, reserves the right to review the necessary information to confirm whether each subject, in the opinion of GSK, meets the required eligibility criteria and may be approved for treatment with mepolizumab under this LAP. Approval will be based on review of the eligibility criteria outlined below, in addition to any other information (if required), with careful consideration of each individual case.

5.1. Inclusion Criteria

Subjects will be required to satisfy the specified inclusion and exclusion criteria requirements listed below to be eligible to receive mepolizumab under the LAP. In addition, GSK may request additional information, not specified here, to support approval of mepolizumab supply.

A subject will be eligible for the LAP only if all of the following criteria apply:

[1] MEA115921 PARTICIPATION
1. Subject participated in study MEA115921

[2] MEA115921 COMPLETION
2. Subject has either :

i. completed study MEA115921 to Week 60, i.e., completion of follow up period, orii. if the subject was withdrawn prematurely from study MEA115921, the subject has reached the date of what would have been the Week 60 if the subject had completed the study, i.e., 60 weeks from Baseline (Visit 2).

[3] SUBJECT REQUIRES PREDNISOLONE (OR EQUIVALENT) ≥ 5 MG/DAY
3. At or up to 6 months after the MEA115921 Week 60 time- point the subject requires a dose of prednisolone (or equivalent) of ≥ 5 mg/day for adequate control of their EGPA.

Note: Inclusion of subjects >6 months after the MEA115921 Week 60 time-point will be considered on an individual subject basis by the GSK Medical Monitor.

[4] PHYSICIAN ASSESSMENT SUPPORTS MEPOLIZUMAB TREATMENT

4. The treating physician requesting mepolizumab under this Long-term Access Programme considers the benefits of treatment with mepolizumab outweigh the risks for the individual subject.

[5] FEMALE SUBJECTS

5. To be eligible for mepolizumab treatment under this Long-term Access Programme, females of childbearing potential (FCBP) must commit to consistent and correct use of an acceptable method of birth control, as summarised in Appendix 2 – Anaphylaxis Criteria

Hypersensitivity reactions will be monitored using the diagnostic criteria for anaphylaxis as outlined by the Joint NIAID/FAAN Second Symposium on Anaphylaxis [Sampson, 2006]. The criteria do not make a distinction based on underlying mechanism. These criteria are summarized as follows:

- 1) Acute onset of an illness (minutes to several hours) with involvement of the skin, mucosal tissue, or both (e.g., generalized hives, pruritus or flushing, swollen lips-tongue-uvula), and at least one of the following:
 - a) Respiratory compromise (e.g., dyspnea, wheeze-bronchospasm, stridor, reduced PEF, hypoxemia)
 - b) Reduced BP or associated symptoms of end-organ dysfunction (e.g., hypotonia [collapse], syncope, incontinence)
- 2) Two or more of the following that occur rapidly after exposure to a likely allergen for that patient (minutes to several hours):
 - a) Involvement of the skin-mucosal tissue (e.g., generalized hives, itch-flush, swollen lips-tongue-uvula)
 - b) Respiratory compromise (e.g., dyspnea, wheeze-bronchospasm, stridor, reduced PEF, hypoxemia)
 - c) Reduced BP or associated symptoms (e.g., hypotonia [collapse], syncope, incontinence)
 - d) Persistent gastrointestinal symptoms (e.g., crampy abdominal pain, vomiting)
- 3) Reduced BP after exposure to known allergen for that patient (minutes to several hours):
 - a) Infants and children: low systolic BP (age specific) or greater than 30% decrease in systolic BP
 - b) Adults: systolic BP of less than 90 mm Hg or greater than 30% decrease from that person's baseline

6. Appendix 3, beginning with consent, for the duration of the treatment with mepolizumab and for 4 months after the last mepolizumab administration.

[6] INFORMED CONSENT

7. The subject consents to receiving treatment with mepolizumab under this Long-term Access Programme.

5.2. Exclusion Criteria

A subject will not be eligible for the LAP if any of the following criteria apply:

[1] MALIGNANCY

1. A current malignancy or history of cancer in remission for less than 12 months (Subjects who had localized carcinoma (i.e., basal or squamous cell) of the skin which was resected for cure will not be excluded).

[2] OTHER CLINICALLY SIGNIFICANT MEDICAL CONDITIONS

2. Subject has other clinically significant medical conditions uncontrolled with standard-of-care therapy not associated with EGPA, e.g., unstable liver disease, uncontrolled cardiovascular disease, ongoing active infectious disease requiring systemic treatment.

[3] PREGNANCY

3. Subject is pregnant or breastfeeding. Subjects should not be considered for continued treatment if they plan to become pregnant during the course of treatment with mepolizumab.

[4] HYPERSENSITIVITY

4. Subject has a known allergy or intolerance to a monoclonal antibody or biologic therapy including mepolizumab.

[5] PREMATURE WITHDRAWAL OF STUDY TREATMENT IN MEA115921

5. Subject had an adverse event (serious or non-serious) considered related to study treatment whilst participating in study MEA115921 which resulted in permanent withdrawal of study treatment.

[6] OTHER BIOLOGICAL THERAPY

6. Subject is receiving treatment with another biological therapy such as a monoclonal antibody therapy or IV immunoglobulin therapy without prior agreement from the GSK Medical Monitor.

[7] OTHER INVESTIGATIONAL PRODUCTS

7. Subjects who have received treatment with an investigational drug within the past

30 days or 5 terminal phase half-lives of the drug whichever is longer, prior to initiation of mepolizumab treatment under this Long-term Access Programme (this also includes investigational formulations of marketed products).

[8] OTHER CLINICAL STUDY

8. Subject is currently participating in any other interventional clinical study.

5.3. Withdrawal/Stopping Criteria

GSK must be advised of any permanent discontinuations of mepolizumab under the LAP. Any subject discontinuing mepolizumab should be assessed 12 weeks after receiving their last dose at a follow-up/end of study visit. If the subject is lost to follow-up an Early Withdrawal form should be completed.

Subjects may continue to receive mepolizumab until any of the following apply:

- The physician determines that the subject is no longer deriving clinical benefit from treatment with mepolizumab or the benefit:risk evaluation does not support continued treatment.
- Subject experiences a treatment-limiting adverse event(s), i.e., an event that results in permanent discontinuation of mepolizumab treatment.
- Subject becomes pregnant or is planning to become pregnant.
- GSK discontinues clinical development of mepolizumab in EGPA. Note, under these circumstances, provision of mepolizumab will be discontinued for all subjects regardless of individual patient benefit received during MEA115921 or 116841.
- Mepolizumab becomes commercially licensed for the treatment of EGPA in the relevant country. UK only clarification: Eligible subjects can continue to receive mepolizumab under this LAP until July 2022.

5.4. Subject and Study Completion

Supply of mepolizumab under the LAP will continue until mepolizumab is commercially available in the relevant country. UK only clarification: Eligible subjects can continue to receive mepolizumab under this LAP until July 2022.

Treating physicians are responsible for the individual benefit:risk assessments and safety monitoring in support of continued mepolizumab treatment.

6. STUDY TREATMENT**6.1. Investigational Product and Other Study Treatment**

The term 'study treatment' is used throughout the protocol to describe open-label mepolizumab supply.

Study Treatment	
Product name:	SB-240563 (mepolizumab)
Formulation description:	Mepolizumab 100mg vial for injection contains target quantities of 10.3mg Sodium Phosphate Dibasic Heptahydrate, 0.96 mg Polysorbate 80 and 230.4mg Sucrose per vial.
Dosage form:	Lyophilized powder for injection reconstituted with Sterile Water for Injection, just prior to use.
Unit dose strength(s)/Dosage level(s):	100 mg/300 mg
Route of Administration:	Subcutaneous injection
Dosing instructions:	Subjects will be dosed with 300 mg SC injection administered as three separate 100 mg SC injections every 4 weeks. Injections should be administered into any of the upper arm, thigh or anterior abdominal wall. It is recommended that individual injection sites are separated by at least 5 cm.
Physical description:	Mepolizumab will be provided as a lyophilised cake in sterile vials for individual use.

Safety monitoring of subjects is required during SC administration and for 1 hour after the end of the injections for the first three administrations, i.e., at baseline, and Weeks 4 and 8. Such monitoring will include general safety monitoring including monitoring for both systemic hypersensitivity (i.e., allergic/IgE-mediated and non-allergic) and local site reactions. From Week 12 onwards, subjects can be monitored following mepolizumab administration in accordance with standard of care at the site.

Trained rescue personnel and rescue medications/equipment must be available for use at all times, see **Error! Reference source not found.** for further information.

6.2. Packaging and Labelling

The contents of the label will be in accordance with all applicable regulatory requirements.

6.3. Preparation/Handling/Storage/Accountability

A description of the methods and materials required for reconstitution of mepolizumab will be detailed in the Study Reference Manual (SRM) which will be accompanied by a Quality Agreement.

- Only subjects enrolled in the study may receive study treatment and only authorized site staff may supply or administer study treatment.
- Mepolizumab must be stored in a secure environmentally controlled and monitored (manual or automated) area in accordance with the labelled storage conditions with access limited to the investigator and authorized site staff.

- The investigator, institution, or the head of the medical institution (where applicable) is responsible for study treatment accountability, reconciliation, and record maintenance (i.e. receipt, reconciliation and final disposition records).
- Study treatment/mepolizumab must be stored in a secure area under the appropriate physical conditions for the product. Access to study treatment will be limited to the investigator's authorized site staff. Mepolizumab must be stored under the appropriate physical conditions which includes storage in a refrigerator or at a temperature of 2-8°C and protected from light. Maintenance of a temperature log (manual or automated) is required. Study treatment must be dispensed or administered only to subjects enrolled in the study and in accordance with the protocol.
- Further guidance and information for final disposition of unused study treatment are provided in the SRM.
- Under normal conditions of handling and administration, study treatment is not expected to pose significant safety risks to site staff. Take adequate precautions to avoid direct eye or skin contact and the generation of aerosols or mists. In the case of unintentional occupational exposure notify the monitor, Medical Monitor and/or GSK study contact.
- A Material Safety Data Sheet (MSDS)/equivalent document describing occupational hazards and recommended handling precautions either will be provided to the investigator, where this is required by local laws, or is available upon request from GSK.

6.4. Treatment of Mepolizumab Overdose

The dose of mepolizumab considered to be an overdose has not been defined. There are no known antidotes and GSK does not recommend a specific treatment in the event of a suspected overdose. The investigator will use clinical judgement in treating the symptoms of a suspected overdose.

6.5. Concomitant Medications and Non-Drug Therapies

6.5.1. Permitted Medications and Non-Drug Therapies

Other concomitant therapy for the treatment of EGPA is permitted.

Use of corticosteroids (excluding inhaled and topical steroids) will be captured.

Concomitant therapy with another biological therapy (e.g., monoclonal antibodies or IV immunoglobulin therapy) should be discussed with the GSK Medical Monitor prior to beginning therapy. If allowed, therapy should not be administered at the same time as the mepolizumab injection(s) and physicians should take measures to separate administration of another biological therapy as long as possible from administration of mepolizumab.

7. ASSESSMENTS AND PROCEDURES

Protocol waivers or exemptions are not allowed with the exception of immediate safety concerns. Therefore, adherence to the assessment requirements, including those specified in the Time and Events Table, are essential and required for study conduct.

This section lists the procedures and parameters of each planned assessment. The exact timing of each assessment is listed in the Time and Events Table Section 7.1.

7.1. Time and Events Table

Visits and Assessments	Screening (up to 4 weeks)	Baseline	Week 4 (±7 days)	Week 8 (±7 days)	Week 12 (±7 days)	Week 16 (±7 days)	Week 20 (±7 days)	Week 24 (±7 days)	Every 4 week treatment cycle/assessments repeated until End of Treatment	Early withdrawal ³	End of Treatment ^{3/} Follow-up (12 weeks post-last dose)
Application Form sent to GSK for approval	X										
Written Informed Consent	X										
Demography and CV risk assessment	X										
Eligibility assessment: inclusion & exclusion criteria review	X										
Baseline information		X									
Dosing with mepolizumab ^{1,2}		X	X	X	X	X	X	X			
Corticosteroid use	X	X	X	X	X	X	X	X		X	X
AE/SAE review	X	X	X	X	X	X	X	X		X	X
Urine pregnancy test (FCBP)	X	X	X	X	X	X	X	X		X	X
Documentation of Benefit:risk evaluation to support continued supply of mepolizumab ¹	X	X			X			X			

1. The treating physician should make a benefit:risk evaluation to confirm continued treatment with mepolizumab is appropriate prior to each administration. This will be documented every 12 weeks to support continued supply. Note: it is expected that the treating physician will monitor subjects as per standard-of-care therapy (including any requirements for blood and urine tests).
2. Safety monitoring of subjects is required during SC administration and for 1 hour after the end of the injections for the first three administrations, i.e., at baseline, and Weeks 4 and 8. From Week 12 onwards, subjects can be monitored following mepolizumab administration in accordance with standard of care at the site.
3. See Section 5.3

7.2. Screening and Critical Baseline Assessments

The subject's informed consent will be obtained at the Screening visit.

Review of inclusion/exclusion criteria will be conducted at the Screening visit.

The investigator will make a benefit:risk evaluation to confirm treatment with mepolizumab is appropriate for the subject.

The subject's identification number from study MEA115921 will be recorded in addition to their current oral corticosteroid dose.

Cardiovascular medical history/risk factors (as detailed in the CRF) will be assessed at screening.

The following demographic parameters will be captured: year of birth, sex, race and ethnicity.

7.3. Safety

Planned time points for all safety assessments are listed in the Time and Events Table (Section 7.1).

The treating physician should make a benefit:risk evaluation to confirm treatment with mepolizumab is appropriate prior to each administration. This will be documented every 12 weeks to support continued supply. It is expected that the treating physician will monitor subjects as per standard-of-care therapy (including any requirements for blood and urine tests).

7.3.1. Adverse Events (AE) and Serious Adverse Events (SAEs)

The definitions of an AE or SAE can be found in Appendix 4. Additionally, because mepolizumab is a monoclonal antibody administered subcutaneously, systemic (i.e., allergic/hypersensitivity and non-allergic) reactions and local injection site reactions will be reported and recorded throughout the treatment and follow-up period. Hypersensitivity reactions will be monitored using the diagnostic criteria for anaphylaxis as outlined by the 2006 Joint NIAID/FAAN Second Symposium on Anaphylaxis [Sampson, 2006] **(Error! Reference source not found.)**.

The treating physician and their designees are responsible for detecting, documenting and reporting events that meet the definition of an AE or SAE.

7.3.1.1. Time period and Frequency for collecting AE and SAE information

- AEs and SAEs will be collected from administration of the first dose of mepolizumab and will continue indefinitely, see minimum schedule of assessments, Time and Events Table (Section 7.1)
- Any SAEs assessed as related to study participation (e.g., protocol-mandated procedures, invasive tests, or change in existing therapy) or related to a GSK product

will be recorded from the time a subject consents to participate in the study up to and including any follow-up contact.

- All SAEs will be recorded and reported to GSK within 24 hours, as indicated in Appendix 4. The treating physician is not obligated to actively seek Aes or SAEs in former study subjects. However, if the investigator learns of any SAE, including a death, at any time after a subject has discontinued mepolizumab treatment under the LAP, and he/she considers the event reasonably related to the study treatment or study participation, the investigator must promptly notify GSK.

NOTE: The method of recording, evaluating and assessing causality of Aes and SAEs plus procedures for completing and transmitting SAE reports to GSK are provided in Appendix 4

7.3.1.2. Method of Detecting Aes and SAEs

Care will be taken not to introduce bias when detecting Aes and/or SAEs. Open-ended and non-leading verbal questioning of the subject is the preferred method to inquire about AE occurrence. Appropriate questions include:

- “How are you feeling?”
- “Have you had any (other) medical problems since your last visit/contact?”
- “Have you taken any new medicines, other than those provided in this study, since your last visit/contact?”

7.3.1.3. Follow-up of Aes and SAEs

After the initial AE/SAE report, the treating physician is required to proactively follow each subject at subsequent visits/contacts. All SAEs, and non-serious Aes of special interest (as defined in Section 4.4.1) will be followed until resolution, until the condition stabilizes, until the event is otherwise explained, or until the subject is lost to follow-up (as defined in Section 5.3). Further information on follow-up procedures is given in Appendix 4.

7.3.1.4. Cardiovascular and Death Events

Investigators will be required to fill out the specific CV event page of the CRF for the cardiovascular Aes and SAEs, as listed in Appendix 4: Section 12.4.3.

In addition, all deaths will require a specific death data collection tool to be completed. The death data collection tool includes questions regarding cardiovascular (including sudden cardiac death) and non-cardiovascular death.

This information should be recorded within one week of when the death is first reported.

7.3.1.5. Regulatory Reporting Requirements for SAEs

Prompt notification by the treating physician to GSK of SAEs and non-serious AEs related to study treatment (even for non- interventional post-marketing studies) is essential so that legal obligations and ethical responsibilities towards the safety of subjects and the safety of a product under clinical investigation are met.

GSK has a legal responsibility to notify both the local regulatory authority and other regulatory agencies about the safety of a product under clinical investigation. GSK will comply with country specific regulatory requirements relating to safety reporting to the regulatory authority, Institutional Review Board (IRB)/Independent Ethics Committee (IEC) and investigators.

Treating physician safety reports are prepared for suspected unexpected serious adverse reactions according to local regulatory requirements and GSK policy and are forwarded to investigators as necessary.

A treating physician who receives an investigator safety report describing a SAE(s) or other specific safety information (e.g., summary or listing of SAEs) from GSK will file it with the IB and will notify the IRB/IEC, if appropriate according to local requirements.

7.3.2. Pregnancy

Urine pregnancy tests in FCBP will be conducted as indicated in the Time and Events Table (Section 7.1).

Details of all pregnancies in female subjects will be collected after the start of dosing and until 12 weeks post last dose. If a pregnancy is reported then the investigator should inform GSK within 2 weeks of learning of the pregnancy and should follow the procedures outlined below.

- Treatment with mepolizumab should be discontinued in the event of pregnancy. .
- Any pregnancy that occurs during study participation must be reported using a clinical trial pregnancy form. To ensure subject safety, each pregnancy must be reported to GSK within 2 weeks of learning of its occurrence. The pregnancy must be followed up to determine outcome (including premature termination) and status of mother and child. Pregnancy complications and elective terminations for medical reasons must be reported as an AE or SAE. Spontaneous abortions must be reported as an SAE.
- Any SAE occurring in association with a pregnancy, brought to the investigator's attention after the subject has completed the study and considered by the investigator as possibly related to the study treatment, must be promptly reported to GSK.

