12.3. Appendix 3 – Acceptable Birth Control

To be eligible for entry into the study, females of childbearing potential (FCBP) must commit to consistent and correct use of an acceptable method of birth control from the time of consent, for the duration of the trial, and for 4 months after the last mepolizumab administration.

- Male partner who is sterile prior to the female subject's entry into the study and is the sole sexual partner for that female subject
- Abstinence from penile-vaginal intercourse.
- UK only clarification: True abstinence from penile-vaginal intercourse when this is in line with the preferred and usual lifestyle of the subject.
- Implants of levonorgestrel or etonogestrel
- Injectable progestogen
- Oral contraceptive (either combined or progestogen alone)
- Estrogenic vaginal ring
- Percutaneous contraceptive patches
- Any intrauterine device (IUD) with a documented failure rate of less than 1% per year.
- Male condom combined with a vaginal spermicide (foam, gel, film, cream, or suppository)
- Male condom combined with a female diaphragm, either with or without a vaginal spermicide (foam, gel, film, cream, or suppository)

Females of childbearing potential are defined as females with functioning ovaries (i.e., post-menarche, premenopausal women with no documented impairment of oviductal or uterine function that would cause sterility). This category includes females with oligomenorrhea, females who are peri-menopausal, and young females who have begun to menstruate (adolescents). The information on the lack of impairment of oviductal or uterine function that would cause sterility can come from the site personnel's:

- Review of subject's medical records
- Medical examination of the subject
- Interview with the subject on her medical history.

Females of non-childbearing potential are defined as females with functioning ovaries and with a documented tubal ligation or hysterectomy; or females who are postmenopausal defined as 12 months of spontaneous amenorrhea with an appropriate clinical profile, e.g. age appropriate, >45 years, in the absence of hormone replacement therapy (HRT).

In questionable cases a blood sample for follicle stimulating hormone (FSH) and estradiol will be obtained and informat to confirm childbearing potential.

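### Pregnancy collection ends 12 weeks after the last dose but contraception is required for 4 months, so a new uncomplicated pregnancy in the final 36 to 39 days has no clearly required report or outcome follow-up

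*Protocol*

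**What the plan says.** **Collection.** Protocol 7.3.2 opens with "Details of all pregnancies in female subjects will be collected after the start of dosing and until 12 weeks post last dose". Its second bullet reads "Any pregnancy that occurs during study participation must be reported using a clinical trial pregnancy form", and goes on to require a report to the sponsor within 2 weeks and follow-up to the outcome for mother and child. Its third bullet covers SAEs associated with a pregnancy that come to light after the subject has completed the study, provided they are "considered by the investigator as possibly related to the study treatment".

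**Contraception.** The inclusion criterion for female subjects (Protocol 5.1) requires contraception from consent, "for the duration of the treatment with mepolizumab and for 4 months after the last mepolizumab administration". Appendix 3 (12.3) repeats it: "for the duration of the trial, and for 4 months after the last mepolizumab administration".

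**Last contact.** Protocol 5.3 says: "Any subject discontinuing mepolizumab should be assessed 12 weeks after receiving their last dose at a follow-up/end of study visit". The Time and Events Table (7.1) puts the last scheduled urine pregnancy test at that visit, or at early withdrawal.

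**Adverse events.** Protocol 7.3.1.1 says "AEs and SAEs will be collected from administration of the first dose of mepolizumab and will continue indefinitely". It then says that the physician need not actively look for events in former subjects. Once treatment under the programme has stopped, mandatory notification is limited to SAEs judged reasonably related to treatment or participation.

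**The concern.** The protocol asks women to avoid pregnancy for 4 months after the last dose, but for the last part of that period it does not clearly ask to hear of one or to learn how it ended. The collection sentence, the last visit and the last pregnancy test all stop at 12 weeks. A test at week 12 cannot detect a later conception. Neither document explains why the two periods differ.

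What is at stake is outcome information on a pregnancy conceived within the sponsor's own precaution period. The study has no hypotheses or endpoints (SAP 2.2 and 2.4), so no estimate or error rate is affected.

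**Working it through.** The plan states no figure for this interval, so there is none to reproduce.

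**1. Length of the gap**
- End of collection: 12 weeks × 7 = 84 days (Protocol 7.3.2).
- End of contraception: 4 months (Protocol 5.1 and Appendix 3). Counted over start dates from 2015 to 2022, four calendar months are 120, 121, 122 or 123 days. The average is 4 × 365.25/12 = 121.75.
- Gap: 120 − 84 = 36 days to 123 − 84 = 39 days; average 121.75 − 84 = 37.75 days.
- Share of the post-dose contraception period: 36/120 = 30% to 39/123 = 32%.

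**2. What covers a pregnancy conceived in the gap, in a woman who has stopped mepolizumab**

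| Provision | Applies? |
|---|---|
| Collection sentence, 7.3.2 | No; it ends at day 84 |
| Form, 2-week report and outcome follow-up, 7.3.2 second bullet | Not on its natural reading. It is limited to study participation, which is undefined, but 5.3 treats the 12-week visit as the end of study |
| SAE linked to the pregnancy and possibly related, 7.3.2 third bullet | Yes, also after completion |
| Complication judged unrelated | Unclear: 7.3.1.1 collects indefinitely but limits mandatory notification after discontinuation to related SAEs |
| Uncomplicated pregnancy as an AE | No; the definitions in 12.4.1 and 12.4.2 do not list it |

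A pregnancy that began before week 12 but surfaced later falls within the collection period and stays reportable. Subjects who move to marketed product are still being dosed (SAP 2.3 design figure), so the gap does not open for them when they leave the programme.

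**3. Expected number**

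Formula: expected pregnancies = N × share stopping × share of childbearing potential × (gap/365.25) × yearly rate.

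From the documents: N = 130, the number randomised in the parent study (Protocol 2.2), and the gap. Assumed: both shares, and a rate of 1% to 5% per year. All rows use the longest gap, 39 days.

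| Share stopping | Share of childbearing potential | Women | Person-years | At 1% to 5% per year |
|---|---|---|---|---|
| 100% | 100% | 130 | 130 × 39/365.25 = 13.88 | 0.14 to 0.69 |
| 100% | 25% | 32.5 | 3.47 | 0.03 to 0.17 |
| 50% | 25% | 16.25 | 1.74 | 0.02 to 0.09 |
| 25% | 25% | 8.1 | 0.87 | 0.01 to 0.04 |

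The first row is a ceiling, not a scenario. Entry requires prednisolone of at least 5 mg/day (Protocol 4.2), so not every parent-study subject qualifies. Some subjects are in compassionate use programme 201607, which ran under its own guidance document (SAP 1 and 7), and section 7.3.2 belongs to MEA116841.

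One factor works the other way. Planning a pregnancy is itself a stopping criterion (Protocol 5.3), so the assumed rate may be too low for some women who stop. In the third row, though, one expected event would need an average of 1/1.74 = 0.57 pregnancies per woman-year across all who stop.

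**The case against.** The strongest objection is textual. Straight after the collection sentence, 7.3.2 says without any time limit that the investigator should tell the sponsor within 2 weeks of learning of a reported pregnancy and then follow the listed procedures, which include outcome follow-up. The second bullet repeats the 2-week duty for each pregnancy. Read broadly, these cover a pregnancy volunteered after week 12. This reading cannot be excluded, and it is why the duty is described as not clearly required. Both sentences, however, follow an explicit limit: 12 weeks in one case, study participation in the other. Even on the broad reading they act only once the site hears of the pregnancy, and nothing asks the woman to report it.

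A second objection is that the two periods need not match: contraception is a precaution, and collection is tied to the last visit. That is fair. The documents give no drug level or half-life for the interval. Appendix 3, in its paragraph on male subjects, reports no reproductive hazard identified in preclinical work. A reader might infer that the gap leaves mother or child at a known risk; the documents do not support that. The point rests only on the protocol's own 4-month precaution.

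A reader might also infer that every pregnancy or complication after week 12 is lost. That is not so, because earlier conceptions and possibly related SAEs stay reportable. Finally, a gap of 112 − 84 = 28 days follows if a month means 4 weeks. The protocol writes weeks where it means weeks, so the calendar reading of 36 to 39 days is the better one.

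**Conclusion.** The mismatch is real and minor. For 36 to 39 days, a new uncomplicated pregnancy in a woman who has stopped mepolizumab has, on the most natural reading, no clearly required report or outcome follow-up. The length of the gap depends only on reading months as calendar months. The expected count is far below one: at most 0.69 under a ceiling that cannot realistically be reached, and 0.01 to 0.17 in the other rows. Those figures rest on assumed shares and an assumed pregnancy rate, neither of which the documents give. No pregnancy display appears in the SAP's list of data displays, so no planned table or listing changes. This is a point to consider, not a defect in the analysis. Confidence is medium because of the untimed sentences in 7.3.2 and because study participation is not defined.

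**What to change.** - In 7.3.2, move the end of pregnancy collection from 12 weeks to 4 months after the last mepolizumab administration.
- In the second bullet, widen the scope to *during study participation or within 4 months after the last dose*, so that the existing form, 2-week report and outcome follow-up apply.
- At the existing 12-week or early withdrawal contact, ask females of childbearing potential who have stopped mepolizumab to tell the site if they become pregnant before 4 months.
- Allow a paper pregnancy report if the electronic tool is already off-line. Section 12.4.6 already gives SAEs a paper or telephone route at that stage.

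Keep the 4-month contraception period, and add no visit or test.

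The cost is two edited sentences, a spoken request at an existing contact, and an occasional late report with outcome follow-up after study completion. Women lost to follow-up would still be missed.
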